8. RISKS AND BENEFITS

List all potential physical, psychological, social, financial or legal risks to subjects (risks listed here should be included on the consent form).

In your opinion, are risks listed above minimal* or more than minimal? If more than minimal, please justify why risks are reasonable in relation to anticipated direct or future benefits.

*(*Minimal risk means the probability and magnitude of harm or discomfort anticipated in the research are not greater than those ordinarily encountered in daily life or during the performance of routine physical or psychological examinations or tests)*

Minimal risks to the subjects are expected. The risks of the testing might include soreness and a temporary increase in skin, muscle, or joint pain. A small risk of a fall during balance testing, physical performance testing, and walking assessments is present. Participants will be free to withdraw from participating in the study at any time if they are uncomfortable with any of the procedures. Although no other risks or changes in the existing minimal risks are anticipated, participants will be informed if any new information arises regarding risks of participation that may affect their decision to continue in the study.

What steps will be taken to minimize risks?

To minimize soreness risks, participants will be asked to complete the minimal number of trials necessary to familiarize individuals with the testing equipment and assessment procedures and obtain a valid test. For balance, physical performance, and walking tasks, participants will be

appropriately supervised by a research member trained in participant guarding to minimize fall risk. The PI will be available by phone during all data collections. The testing done within the context of this study is used on a daily basis in the clinical setting, except that patients typically do not receive assessment of O₂ consumption during walking.

Describe any potential direct benefits to participants.

Investigators will review results of blood pressure screening with each participant and review the results of each participants' functional performance testing. If the vital sign screening indicates a need for an immediate referral, the examiner will contact the primary care provider and the patient will not be eligible to participate in further testing. Participants will be given blood pressure screening and physical performance handouts to share with their medical providers.

Describe any potential future benefits to this class of participants, others, or society.

Potential benefits include establishment of speed (mph) and cadence (steps/min) for sedentary adults with lower-limb amputations that corresponds to 3 METs, i.e. moderate-intensity physical activity, which may be used when initiating an exercise program to enhance physical activity. It is possible that a physical activity questionnaire will be found to be reliable and valid for this patient population for assessment of physical activity, which will aide clinicians in evaluation of patients with limb loss. Objective data assessing the additional energy expenditure necessary for inactive adults with a lower-limb amputation to walk short-distances using a prosthesis may provide useful information for the development of future prosthetic components to reduce energy expenditure. Preliminary data evaluating modifiable factors related to energy expenditure and physical activity may help to inform future research studies.

If there is a Data Monitoring Committee (DMC) in place for this project, please describe when and how often it meets.

As this is a small project, there will not be a data monitoring committee. The Principal Investigator ([name]) will provide ongoing review of the accrued research data to ensure the safety of research participants and the provisions for protecting the privacy of participants and the confidentiality of research data.

[name], if not present during the on-site evaluations, will be made aware of any unexpected or adverse events immediately via phone. If an adverse event occurs, it will be reported immediately by a Principal Investigator to the University of Delaware Institutional Review Board (IRB) in accordance with the IRB's stated policy for reporting adverse events in the IRB reference manual.

The Principal Investigator will review subject recruitment and accrual with the research personnel conducting phone screenings on a monthly basis. The validity and integrity of the research data will be reviewed quarterly by the Principal Investigator. Ongoing review of scientific literature, related to the research will be performed by the Principal Investigator, to determine if changes to the study should be made given new information.

9. COMPENSATION

Will participants be compensated for participation?

Yes

If so, please include details.

Compensation will be provided to all participants for their time and participation in the study after the individual returns the electronic monitor(s) as monitor replacement costs exceed the \$40 honorarium that will be given to participants. Compensation was determined based upon the time required for evaluation and wearing the step activity monitor for 7 days, as well as travel expenses to the onsite

evaluation. If participants do not complete all questionnaires and components of the on-site examination and 7-day activity monitoring, e.g. they complete some components but choose not to complete other components or they wear the monitor for less than 7 days, then their compensation will still be \$25 (assuming that the activity monitor(s) is/are returned).

10. DATA

Will subjects be anonymous to the researcher? No

If subjects are identifiable, will their identities be kept confidential? (If yes, please specify how)

Consent to contact forms, telephone demographics sheets, informed consent forms, and a copy of the participant's handouts will be secured in locked cabinets within the Department of Physical Therapy and will accessible only to research personnel. Names and contact information will be entered into an electronic database that will be stored on a password protected University maintained sever with regular and secured back-ups. A separate electronic database with the participant's name and contact information will be stored on a password protected University maintained server with regular and secured back-up if he/she agrees to be contacted for future studies.

How will data be stored and kept secure (specify data storage plans for both paper and electronic files. For guidance see <http://www.udel.edu/research/preparing/datasstorage.html>)

All paper research records will be maintained in the Department of Physical Therapy ([name]). Paper files will be secured in locked cabinets. De-Identified data will be entered from the paper records to a computerized database where all patients will be identified by a code number only. Research information will be indefinitely stored using a coded number. Only research personnel will have access to this data. There will be a single file linking participant name to number, which will be password protected and stored on a secured server, where only research members have access. Coded electronic data will be securely stored on a password-protected departmental server, as well as portable electronic devices that are securely stored in locked cabinets within the Department of Physical Therapy.

How long will data be stored? Data will be stored indefinitely.

Will data be destroyed? YES NO (if yes, please specify how the data will be destroyed)

Will the data be shared with anyone outside of the research team? YES NO (if yes, please list the person(s), organization(s) and/or institution(s) and specify plans for secure data transfer)

How will data be analyzed and reported?

Analyzed

Analyses will be performed using SPSS statistical software packages with consultation of an experienced biostatistician (when needed). Descriptive statistics will be used to characterize the study sample.

Specific Aim 1: To determine reliability, intra-class correlation coefficients (ICCs) with 95% confidence intervals (CIs) will be calculated to evaluate test-retest reliability of physical activity

questionnaires. To evaluate validity between the self-report questionnaire data and activity-monitor obtained data that is continuous (e.g. steps/day, total activity in minutes/day), we will use ICCs with 95% CIs. We will quantify the relationship between the self-report data and activity-monitor data using Spearman's correlation coefficients. Interpretation will be as follows: $p \leq .25$ =weak correlation, $p=.26\text{--}.49$ =low correlation, $p=.50\text{--}.69$ =moderate correlation, $p \geq .70$ =high correlation.

Specific Aim 2: We will use receiver operating characteristic (ROC) curves to determine the minimal speed and cadence that corresponds to an oxygen consumption value of 10.5 mL/kg/min (i.e. 3.0 METs), as this has been identified by the World Health Organization as 'moderate intensity' activity.¹⁰

Specific Aims 3 and 6-10: We will use a MANOVA/MANCOVA to evaluate between-group differences with follow-up ANOVAs/ANCOVAs as appropriate ($p \leq 0.05$).

Specific Aims 4/5: Regression models will be used to explore relationships between energy expenditure (or average daily step counts) and each of the modifiable factors of interest, while controlling for relevant non-modifiable covariates, e.g. age, residual limb length.

Reported

Dissemination of results will occur through conference presentations and manuscript publications in peer-reviewed journals.

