5. RESEARCH ABSTRACT

Please provide a brief description in LAY language (understandable to an 8th grade student) of the aims of this project.

Up to 48% of adults following a lower-limb amputation will die within the upcoming year.¹ Lack of physical activity (exercise) contributes to high death rates.^{2,3} It is recommended that younger (and middle-aged) adults without a health condition walk 10,000 steps/day to reduce the risk of chronic health conditions, while recommendations are 7,100 steps per day for older adults and those with chronic health conditions.⁴ Adults with a lower-limb amputation walking about 21-43%⁵⁻⁷ of the recommended 7,100 steps/day.⁴ Step activity monitors, such as the StepWatch (a research-grade accelerometer) and the FitBit (a commercially-available monitor) provide a means of evaluating physical activity, which is important since patients tend to over-estimate their level of physical activity.^{8,9} Activity monitor use, however, may not be possible in every healthcare practice setting, as monitors may cost \$100-\$600 and someone must remove the data from the monitor, interpret the

data, and enter the data into the patient's medical record. Therefore, physical activity questionnaires, where the patient self-reports their physical activity, are ideal in a clinical setting. Unfortunately, to date, there has been little research looking at the accuracy of physical activity questionnaires in patients with lower-limb amputations and how these questionnaires measure up to data obtained from step activity monitors.

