We will provide the first objective data that looks at the additional energy expenditure necessary for inactive adults with a lower-limb amputation who are using a prosthesis to walk short-distances as compared to able-bodied adults; this data may be used for the development of future prosthetic components that reduce energy expenditure. We will explore factors that may be linked to energy expenditure and physical activity among adults with and without a lower-limb amputation.

Specific Aim 1: Evaluate reliability and validity of physical activity self-report measures (i.e. International Physical Activity Questionnaire, Incidental and Planned Exercise Questionnaire-past week^{23,24}) as compared to physical activity characteristics obtained via step activity monitors (i.e. time spent walking/day, walking bout duration, walking bouts/day) among inactive adults with a single-limb amputation (n=20).

Hypothesis: *H1a: Both self-report measures will have excellent test-retest reliability (ICCs $\geq .75$). H1b: At least 1 self-report measure will demonstrate validity with ≥ 2 physical activity characteristics.*

Specific Aim 2: Determine what gait speed (mph) and cadence (steps/minute) constitute 3 METs, i.e. moderate-intensity activity, among inactive adults with a single, below-the-knee amputation during over-ground and treadmill walking (n=20).

Hypothesis: *H2a: 3 METs will occur at slower speeds during treadmill walking as compared to over-ground walking. H2b: 3 METs will occur at slower cadences during treadmill walking as compared to over-ground walking.*

Specific Aim 3: Evaluate differences in energy expenditure based on oxygen consumption between inactive adults with a single, below-the-knee amputation (n=20) and matched controls (n=20) during short bouts of over-ground and treadmill walking at self-selected gait speeds, 75% and 125% of self-selected gait speeds.

Hypothesis: *H3: Energy expenditure will be significantly greater at all walking speeds for adults with a limb amputation as compared to controls (a) over-ground and (b) during treadmill walking ($p \leq 0.05$).*

Specific Aim 4: Explore modifiable factors that may impact energy expenditure (assessed via oxygen consumption) including comorbidities, fatigue, sleep disturbance, balance, functional lower extremity strength, functional mobility, and agility among adults with (n=20) and without a unilateral below-the-knee amputation (n=20).

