5. Patient-Reported Outcomes Measurement Information System (PROMIS-29): The PROMIS-29 is a subset of the PROMIS assessment of self-reported health²⁹ that measures quality of life based on physical function, pain interference, fatigue, sleep disturbance, anxiety, depression, and social participation.^{30,31} Individuals with lower-limb loss have been shown to score significantly lower on physical function, pain interference, and participation in social role subscales when compared to individuals without lower limb amputation.³¹
6. International Physical Activity Questionnaire – Long Form (IPAQ)*: The questionnaire, designed for adults ages 18-65, consists of 31 items assessing physical activity in four domains: transportation, work, household and gardening tasks, and leisure time.³³ It is a valid and reliable measure of self-reported physical activity level in healthy adults³⁴; however, psychometric properties have not been established for use in individuals with lower-limb amputation. We will use this measure to compare self-reported physical activity levels to objective physical activity characteristics obtained from 7-days of monitoring via step-activity monitors.
7. Incidental and Planned Exercise Questionnaire-past week*: This questionnaire has 10 items that ask about exercise type, intensity, and duration in the past week.

*These 2 questionnaires will be provided to the participant at the end of the on-site evaluation. Participants will be asked to re-complete these questionnaires at the end of their 7 days of activity monitoring and return in the envelope with the step activity monitor and activity monitor log. It is projected that re-completion of these 2 questionnaires will take < 10 minutes.

Individuals with lower-limb amputations will also complete the following:

8. Houghton Scale of Prosthetic Use⁴⁸: The questionnaire has 4 items related to wear duration, use, and perceived stability.²⁸ Total scores range from 0-12 with higher scores indicating better function.²⁸ Scores $\geq 9/12$ suggest the individual is a community-ambulator. This questionnaire will help to characterize the participants with limb-loss in our sample.

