Upon completion of the on-site evaluation, participants will be sent home with the activity monitor for a 7-day activity observation period. Participants will be instructed to perform their regular daily activities, wearing the monitor at all times that they are wearing their prosthesis. During the observation period, the activity monitor will record the number of steps the participants take. Participants will be provided with a pre-paid and addressed padded envelope and instructed to mail the activity monitor back after 7 days. Upon return of the monitors, study investigators will extract the step count data from the activity monitors. The 2 physical activity questionnaires will also be sent back re-completed (after 7 days) in these pre-paid envelopes, which will allow us to evaluate test-retest reliability of these questionnaires.

Review of Data. We will discuss and provide participants with blood pressure data, and physical performance data via written handouts (uploaded) at the conclusion of their on-site examination.

Participants with inappropriate vital signs will be managed in accordance with the policies outlined on the blood pressure screening handout; when necessary, the examiner will contact the provider.

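### Aim 1 plans a validity ICC for pairs that may be in different units (steps/day against a questionnaire score); its size then depends on the scoring unit as well as on the correlation

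*Combined protocol and SAP*

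**What the plan says.** Section 10 (Specific Aim 1) has three steps. The first is an ICC for test-retest reliability of the questionnaires. The second is a separate ICC for validity against the monitor: for "activity-monitor obtained data that is continuous (e.g. steps/day, total activity in minutes/day), we will use ICCs with 95% CIs". The third is a rank correlation: "We will quantify the relationship between the self-report data and activity-monitor data using" Spearman coefficients, followed by four bands (up to .25 weak, .26 to .49 low, .50 to .69 moderate, .70 and above high). The form of the ICC (consistency or agreement, single or average measures) is not given.

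Section 6 describes what is being compared. The IPAQ "consists of 31 items assessing physical activity in four domains: transportation, work, household and gardening tasks, and leisure time". Of the other instrument it says: "This questionnaire has 10 items that ask about exercise type, intensity, and duration in the past week". On the monitor side, "the activity monitor will record the number of steps the participants take". No scoring unit, conversion or standardisation is stated for either questionnaire.

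Section 5 lists the monitor characteristics for Aim 1 as "time spent walking/day, walking bout duration, walking bouts/day". H1b requires at least one questionnaire to show validity with two or more of these. It names no statistic and no cut-off. The ICC threshold of .75 in H1a is for test-retest reliability only.

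**The concern.** An ICC compares two measurements of one quantity on one scale. Steps/day is the first example that Section 10 gives for the validity ICC, yet nothing in the documents puts a questionnaire score on a step scale. Scoring the same answers per day or per week would change the ICC and its confidence interval, although the respondents said nothing different.

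The stake is the reading of the Aim 1 validity result. A questionnaire that ranks participants well could be reported with an ICC near zero because of its unit. Two questionnaires scored in different units could also be ranked wrongly against each other. Section 5 lists a self-report measure usable in clinical practice as the first intended product of the project.

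**Working it through.** The plan gives no expected ICC, power or precision figure for Aim 1, so there is no figure to reproduce. The check is algebra plus an illustration.

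**Formulas.** Let r be the correlation, s1 and s2 the SDs, m1 and m2 the means, and k = s1/s2. For single measures:

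- Consistency ICC = 2·r·s1·s2/(s1² + s2²) = 2rk/(1+k²).
- Agreement ICC = r·s1·s2 / [(s1² + s2²)/2 + (m1 − m2)²/2].

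At r = 1 the consistency form cannot exceed 1.00 for k = 1, 0.80 for k = 2, 0.38 for k = 5, 0.20 for k = 10 and 0.02 for k = 100. This needs no assumption about the trial. Because 2k/(1+k²) never exceeds 1, a single-measure ICC lies at or below a positive r.

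**Inputs for the illustration.**

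- Steps/day, from Section 5: "Adults with a lower-limb amputation walking about 21-43" percent of 7,100. That is 0.21 × 7,100 = 1,491 to 0.43 × 7,100 = 3,053, with midpoint 2,272.
- Assumed, not in the documents: r = 1; SD/mean = 0.5; questionnaire mean 30 (minutes/day), 7 × 30 = 210 (the same answers in minutes/week), or 1,500 (an arbitrary larger score).

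**One case in full: 2,272 against 30.** s1 = 1,136 and s2 = 15, so s1·s2 = 17,040. (1,136² + 15²)/2 = 645,360.5. (2,272 − 30)²/2 = 2,513,282. Consistency = 17,040/645,360.5 = 0.026. Agreement = 17,040/3,158,642.5 = 0.0054.

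| Score mean | Agreement ICC | Consistency ICC | Spearman |
|---|---|---|---|
| 30 | 0.005 | 0.026 | 1.0 |
| 210 | 0.043 | 0.183 | 1.0 |
| 1,500 | 0.696 | 0.920 | 1.0 |

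A simulation with n = 20 and log-normal data at r = 1 gives median agreement ICCs of 0.005, 0.039 and 0.67.

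**Range over the assumptions (agreement ICC for 30, 210, 1,500).**

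- SD/mean 0.3: 0.002, 0.018, 0.486. SD/mean 0.8: 0.010, 0.081, 0.817.
- 1,491 steps/day: 0.008, 0.071, 1.00. 3,053 steps/day: 0.004, 0.031, 0.432. The 1.00 arises only because 1,491 happens to lie next to 1,500.
- r = 0.7 (2,272 steps/day, SD/mean 0.5): 0.004, 0.030, 0.487.

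**Order can reverse between units.** With r = 0.3 and the 1,500 score, consistency = 0.3 × 0.920 = 0.28. With r = 1 and the 30 score it is 0.026.

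**Average measures.** The average-measures consistency ICC is 2C/(1+C), where C is the single-measure value. For C = 0.276 it is 0.552/1.276 = 0.43, above the correlation of 0.3. The upper bound above therefore does not cover this form, and the plan does not say which form it will use.

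**Same-unit contrast.** If a questionnaire reports exactly double the monitor minutes (30 against 60, SD/mean 0.5), s1·s2 = 15 × 30 = 450. Agreement = 450/[(225 + 900)/2 + 30²/2] = 450/1,012.5 = 0.44, while Spearman is 1.0. Here the ICC reports something that Spearman cannot.

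**The case against.** The strongest reply is that Spearman correlations are also planned, do not depend on units and come with interpretation bands. The aim therefore keeps one readable measure, and an ICC of 0.005 beside a high Spearman would look odd enough to be questioned. This stands, and it limits the consequence. It does not repair the ICC: Section 10 attaches the word validity to the ICC, and H1b does not say which statistic decides if the two conflict. The bands narrow that gap without closing it, because no band is named as sufficient for validity.

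A second reply is that the questionnaires are separate uploads and may be scored in minutes. That is possible, and for monitor minutes/day the ICC would then be suitable in principle. It does not help for steps/day, which the text names without restriction.

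A reader might infer more than the documents support:

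- *That the ICC says nothing about validity.* At a fixed unit it rises in proportion to the correlation: for the 1,500 score, agreement falls from 0.696 at r = 1 to 0.487 at r = 0.7.
- *That mixed units could make a weak questionnaire look strong.* A single-measure ICC cannot exceed the correlation, so the error runs towards understatement. Only an average-measures form escapes that bound.
- *That the steps/day ICC decides H1b.* Steps/day is not among the characteristics listed under Aim 1 in Section 5. Bout duration and bouts/day are listed and would have the same problem, but only if the ICC is applied to them, which Section 10 does not say.

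**Conclusion.** The validity ICC is wrong as written for any pair in different units, and steps/day is named as such a case. Its value mixes the correlation with the choice of scoring unit, and in single-measure form it understates validity by an amount that the unit sets. The closed form establishes this without assumptions. The sizes shown (agreement ICC from 0.005 to 0.70 at perfect correlation) are illustrative, because the documents do not give scoring units, means or SDs; they are not predictions of this study's results.

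The effect is confined to the Aim 1 validity analysis. Reliability, the other aims and the data collected are untouched, and the planned Spearman results would still be available. It would be wrong to conclude that Aim 1 validity cannot be assessed, or that ICCs should be removed altogether. Section 5 notes that "patients tend to over-estimate their level of physical activity", and a same-unit agreement ICC can detect this where Spearman cannot. The point should be fixed before analysis.

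**What to change.** In Section 10, Specific Aim 1:

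1. Limit the validity ICC to pairs in the same unit, such as questionnaire minutes/day against monitor minutes/day, and state its form (absolute agreement, single measure).
2. For steps/day, and for any other variable in a different unit from the questionnaire score, report no ICC. Base validity on the Spearman correlation and bands already planned.
3. State for each type of pair which statistic, and which band or cut-off, decides H1b. For same-unit pairs the choice is the investigators', bearing in mind that Spearman does not detect systematic over-reporting.

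Optional additions are a Bland-Altman plot for same-unit pairs, a 95% CI for Spearman, and a statement of which activity domains each side counts. The last is useful because a shared unit does not guarantee a shared construct.

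Cost: two or three sentences in the analysis plan, with no change to data collection.

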Walking exercise may occur over-ground or on a treadmill. When an individual with a lower-limb amputation is walking over-ground, their right-to-left side walking pattern will be more asymmetrical (uneven) when compared to when they are walking on a treadmill.¹⁶ When walking is more symmetrical side-to-side (even), the patient may have to expend more energy. Energy expenditure can be assessed as the amount of oxygen consumed, which can be obtained while wearing a mask that evaluates your breathing while walking. Among adults with a lower-limb amputation, energy expenditure studies have generally used treadmills to look at energy expenditure.¹⁷⁻²⁰ Over-ground versus treadmill conditions, however, are different,²¹ and as such, what equals 3 METs (speed, cadence) in each walking condition may vary.²²

Further, no studies have compared the energy cost of walking in adults who are inactive with a lower-limb amputation to age-, sex-, and body mass index (computed from height and weight) - matched adults without an amputation. While studies have evaluated the impact of aging^{52,53} and limb length of the amputated limb^{49,51} on energy expenditure, few have evaluated modifiable factors that may impact energy expenditure among adults with lower-limb amputation.^{56,57} Similarly, little research has explored modifiable factors that may impact physical activity levels.^{54,55}

The project's goal is to provide knowledge that will improve physical activity prescription for inactive adults with a single, below-the-knee amputation (i.e. transtibial amputation).

Successful completion of the project may provide healthcare providers with (1) a physical activity self-report measure that can be used in clinical practice for patients with a lower-limb amputation, (2) gait speed (mph) for prescribing moderate-intensity over-ground and treadmill walking during the rehabilitation of patients with lower-limb amputations, and (3) cadence (steps/minute), for evaluating and monitoring moderate-intensity physical activity via step activity monitors, for inactive adults with a lower-limb amputation.

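### Aim 2 plans only ROC curves, with no cut-off rule, interval or paired treadmill versus over-ground contrast, so its answer can move with the speeds tested

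*Combined protocol and SAP*

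**What the plan says.** Section 5 (RESEARCH ABSTRACT) sets Aim 2: "Determine what gait speed (mph) and cadence (steps/minute) constitute 3 METs" in 20 adults with a transtibial amputation, over-ground and on a treadmill. Two directional hypotheses follow: "H2a: 3 METs will occur at slower speeds during treadmill walking as compared to over-ground walking" and "H2b: 3 METs will occur at slower cadences during treadmill walking as compared to over-ground walking". The rationale is that "what equals 3 METs (speed, cadence) in each walking condition may vary". One intended product is "gait speed (mph) for prescribing moderate-intensity over-ground and treadmill walking during the rehabilitation of patients with lower-limb amputations"; another is a cadence for use with step monitors.

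The whole Aim 2 analysis is one sentence in section 10 (DATA): "We will use receiver operating characteristic (ROC) curves to determine the minimal speed and cadence that corresponds to an oxygen consumption value" of 10.5 mL/kg/min. The other methods there are assigned elsewhere. The ICCs with 95% CIs belong to Aim 1. The rest reads "Specific Aims 3 and 6-10: We will use a MANOVA/MANCOVA to evaluate between-group differences" and "Specific Aims 4/5: Regression models will be used to explore relationships between energy expenditure".

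Section 6 (PROCEDURES) gives three stages per condition. Treadmill stages are set at 75, 100 and 125% of self-selected speed. Over-ground stages follow instructions to walk slowly, at a usual comfortable pace, and briskly, with distance recorded. VO2 and step counts are collected at every stage.

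**The concern.** An ROC curve lists every possible cut-off and selects none. The word minimal in the Aim 2 sentence does not select one either. It could mean the lowest speed with full sensitivity, the best-balanced cut-off, or the speed at which average VO2 crosses 10.5, and these are different quantities.

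Common balanced rules also tie the cut-off to the mix of stages tested. Treadmill and over-ground speeds are set in different ways, so the two conditions can give different cut-offs when the VO2-speed relation is the same in both. H2a and H2b would then be judged by comparing two such numbers, with no interval and no paired test. At stake are the speed offered for prescribing walking and the answer to both hypotheses.

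**Working it through.** The documents give no cut-off, interval or power figure for Aim 2, so there is nothing to reproduce. The check has four steps.

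**1. What a Youden cut-off estimates.** Youden's rule picks the speed v where the density of v is equal among stages at or above 10.5 and stages below it. By Bayes' rule this is the v where P(VO2 ≥ 10.5 | v) = p, with p the overall share of stages at or above 10.5. Suppose VO2 = 10.5 + b(v − v0) + person effect + residual, with σ² the sum of the two variances. Then, in large samples:

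Youden cut-off − v0 = (σ/b) × Φ⁻¹(p).

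It equals v0 only if p is one half. An accuracy-maximising rule solves P = ½ and so does not depend on p in this way.

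**2. Inputs.** From the documents: pilot self-selected speeds of 0.88 m/s (K3) and 1.16 m/s (K4), the 75/100/125% stages, and the reported 3-MET speed of 1.47 mph (1.47/2.23694 = 0.657 m/s). The investigators believe 1.47 mph is above 3 METs for their patients. Section 5 also says maximal speed after limb loss from poor circulation may be no more than 1.67 mph. If that caps the 125% stage, self-selected speed is at most 1.67/1.25 = 1.34 mph, or 0.60 m/s.

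Assumed, not in the documents: b = 6 to 10 mL/kg/min per m/s, between-person SD 1 to 2, residual SD 0.7 to 1.2, self-selected speed SD 0.2 m/s.

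**3. One condition, 20 people × 3 stages.** Worked case at K3 with b = 10 and SDs 1 and 0.7. The chances of falling below 10.5 in the three stages are 0.49, 0.17 and 0.06, so about 20 × 0.72 = 14.4 of 60 stages are below. Then p = 0.76, Φ⁻¹(p) = 0.706 and σ/b = √(1 + 0.49)/10 = 0.122. The shift is 0.122 × 0.706 = 0.086 m/s = +0.19 mph. With b = 6 and SDs 2 and 1.2, 19.4 stages are below, p = 0.676, and the shift is 0.389 × 0.457 = 0.178 m/s = +0.40 mph.

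| Self-selected speed | Mean stages (mph) | True 3-MET speed | Youden error, simulated (mph) | Formula, two corners (mph) |
|---|---|---|---|---|
| 0.88 m/s (K3) | 1.48, 1.97, 2.46 | 1.47 | about +0.15 to +0.4 | +0.19, +0.40 |
| 1.16 m/s (K4) | 1.95, 2.59, 3.24 | 1.47 | about +0.3 to +0.8 | +0.45, +0.87 |
| 0.70 m/s (assumed) | 1.17, 1.57, 1.96 | 1.47 | +0.02 to +0.09 | +0.02, +0.07 |
| 0.60 m/s | 1.01, 1.34, 1.68 | 1.47 | -0.12 to -0.07 | -0.07, -0.12 |
| 0.60 m/s | as above | 1.2 | about +0.05 to +0.13 | +0.05, +0.11 |
| 0.88 m/s (K3) | as above | 2.0 | -0.05 to -0.03 | -0.03, -0.04 |

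At K4 only 3 to 9 of 60 stages lie below 10.5, so the large-sample formula overstates the simulated error. With a true 1.2 mph at K4, up to 42% of simulated studies had no stage below 10.5 and hence no ROC curve.

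At K3 with 1.47 mph, closest-to-corner is off by +0.14 to +0.33 mph, close to Youden. The accuracy-maximising rule is off by -0.01 to +0.02 (SD 0.11 to 0.27), and inverse prediction from a random-intercept regression by -0.02 to 0.00 (SD 0.06 to 0.20). On the same data, Youden and accuracy-maximising differ on average by 0.16 to 0.37 mph. A bootstrap 95% interval around the Youden cut-off contains the mean crossing in about 28 to 59% of studies, so an interval alone does not repair it.

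For cadence at K3 (true 86 steps/min; assumed 30 to 45 steps/min per m/s, between-person SD 5 to 8), the errors are +3.5 to +8.2 steps/min for Youden, -6.7 to -0.9 for accuracy-maximising and -3.5 to -0.3 for regression.

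**4. The contrast behind H2a.** K3 speeds, assumed person-by-condition SD 0.7 to 1.0, and four assumed over-ground speed mixes. With an illustrative true difference of 0.20 mph (over-ground minus treadmill), the Youden difference averages -0.16 to +0.18 and is zero or wrong-signed in 11 to 74% of studies. The regression difference averages 0.19 to 0.22 and is zero or wrong-signed in 0 to 14%. With no true difference, 0.2 mph is exceeded in 17 to 56% of studies by Youden and 0 to 28% by regression.

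**The case against.** The strongest reply is about the target. The plan never says it wants the speed at which mean VO2 is 10.5, so calling a Youden cut-off too high presumes that target. With between-person SD of 1 to 2 mL/kg/min, about half of people walking at the mean crossing are below 3 METs, so the mean crossing is itself a choice. This stands: the errors are conditional on it. It also confirms that the plan leaves its target undefined.

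Second, H2a and H2b carry no significance criterion, unlike H3 and Aims 6-10, so a descriptive comparison is a possible reading. But Aim 2 is not labelled exploratory (Aims 4 and 5 are), and a descriptive comparison of directional hypotheses still needs an interval and a method that isolates the condition.

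Third, the remedy is larger than naming a rule, adding an interval and adding a paired contrast, and the plan specifies SPSS. That is fair as to cost. Those minimal steps would not remove the dependence on the speeds tested if the named rule were Youden or closest-to-corner.

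A reader might draw three stronger conclusions, which the documents do not support:
- That the ROC cut-off will be too high. Section 5 itself describes slow walkers. At 0.60 m/s the Youden error is about -0.1 mph with a 1.47 mph threshold and small with 1.2 mph. The pilot patients are not said to be inactive, so K3/K4 speeds may not apply.
- That any two analysts would differ by 0.2 to 0.4 mph. That gap is Youden against accuracy-maximising at K3. Youden and closest-to-corner nearly agree, with medians 0.01 to 0.05 mph apart.
- That ignoring the three stages per person badly distorts the interval. Resampling stages or people gives nearly the same SD for the Youden cut-off (0.11 to 0.23 mph).

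**Conclusion.** The point holds as an under-specified analysis that should be fixed. The missing rule, interval and paired contrast are plain from the text and rest on no assumption. That a Youden or closest-to-corner cut-off moves with the share of stages reaching 10.5 is a property of those rules. Because the two conditions use different speed mixes, a difference between such cut-offs cannot be attributed to the walking condition.

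The size is uncertain. It depends on the assumed VO2 slope and variability, on a mean-crossing target, and above all on how fast participants walk relative to their 3-MET speed. On the documents' own figures it ranges from about -0.1 mph (slow walkers) through near zero to about +0.8 mph (K4 pilot speed), with about +0.15 to +0.4 mph at K3. ROC is not invalid as such: it suits classifying monitor minutes by cadence once its rule is named.

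**What to change.** In section 10, replace the Aim 2 sentence with the following:

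- **Target:** the speed, and separately the cadence, at which mean VO2 equals 10.5 mL/kg/min in each condition.
- **Main analysis:** a mixed model of continuous VO2 on actual speed (treadmill setting; over-ground distance divided by stage time), by condition, with test order and with participant and participant-by-condition effects. Repeat it with cadence. Solve for the value at 10.5, with a participant-level 95% CI.
- **Curve form and fallback:** pre-specify both, for example a quadratic as main and a straight line as sensitivity, and state what is reported if the curve does not reach 10.5.
- **H2a/H2b:** the within-person treadmill minus over-ground difference in that value, with its CI.
- **Reporting:** the number of stages below 10.5 in each condition, with estimates outside the tested speeds flagged.
- **ROC:** secondary, for monitor-based cadence classification, with a named rule, sensitivity, specificity and a participant-level interval.

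The cost is wording and a little more analysis, possibly outside standard SPSS menus. No extra data or participant burden is needed.

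Downsides:
- The answer depends on the VO2-speed shape. If VO2 follows speed squared, a straight line is off by -0.10 to +0.12 mph at K3 or slower speeds and about +0.2 at K4. A quadratic brings the median within 0.03 mph but has no solution in 0 to 12% of simulated studies.
- With 20 people the contrast stays imprecise: in the settings run, power for a 0.20 mph difference was 21 to 84% with the quadratic.
- Cadence regression is not free of bias (up to -3.5 steps/min at K3).
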